4.5.2 Concomitant Medications

Concomitant medications are defined as any medication taken on or after the date of the first dose of study drug.

In order to ensure that appropriate concomitant therapy is administered, it is essential that subjects be instructed not to take any medication without prior consultation with the Investigator (unless the subject is receiving treatment for a medical emergency).

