4.5.2.1 Permitted, Restricted, and Prohibited Medications

Prohibitions and restrictions for concomitant medications should be followed between the initial Baseline visit and Visit 9/ET as specified in [Appendix A](#) and [Appendix B](#). These appendices do not constitute an exhaustive list and any questions regarding prohibited and restricted medications should be discussed with the Medical Monitor or designee.

Use of medications that could interfere with study conduct or any questions regarding prohibited and restricted concomitant medications should be reviewed and/or discussed with the Medical Monitor or designee.

Medications that can prolong QT interval are prohibited (or restricted if approved by the Medical Monitor) as specified in [Appendix A](#).

If a subject is on a medication restricted by the protocol, the medication should be adjusted if it is determined by the Investigator to be clinically appropriate (e.g., if the subject's symptoms are not well-controlled or if the subject cannot tolerate the current medication) in consultation with the treating physician.

The Investigator may prescribe, adjust, or discontinue appropriate medication to treat or manage AEs. Subjects who require current treatment with a prohibited medication will be withdrawn from the study.

Subjects who have previously taken a prohibited medication during the study will be withdrawn from the study unless:

- the prohibited medication has been discontinued AND

- withdrawal from the study presents an unacceptable medical risk to the subject

The justification to allow the subject to continue in the trial will be made by the Sponsor/Medical Monitor, with medical input from the Investigator, and will be documented. If a subject is allowed to remain in the trial, this will be reported as a major protocol deviation and not a waiver.

Permitted concomitant medications should remain at a stable dose throughout the study. Benzodiazepines (lorazepam up to 1 mg/day or equivalent) are allowed as rescue medication as needed for severe neuropsychiatric or behavioral disturbances ([Appendix A](#)).

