	RESTRICTED 
 • zaleplon • ramelteon 	
 • May not be used within 12 hours of a cognitive assessment, and efforts should be made to limit agents to lowest dose for the shortest time needed.
Stimulants and wake-promoting agents	PROHIBITED 
 • methylphenidate • modafinil • armodafinil • amphetamine 	
 • Prohibited at study entry and throughout the study
Non-stimulant ADHD medications	PROHIBITED 
 • atomoxetine 	
 • Prohibited at study entry and throughout the study
Serotonin antagonists	PROHIBITED 
 • cyproheptadine 	
 • Prohibited throughout the study • Must be discontinued at least 3 weeks prior to the Baseline visit
Antiarrhythmic drugs	PROHIBITED 
 • ajmaline • amakalant, semantilide • amiodarone • bretylium • disopyramide • dofetilide • dronedarone • flecainide • ibutilide • procainamide • propafenone • quinidine • sotalol, d-sotalol 	
 • Prohibited at study entry and throughout the study
Opioids	PROHIBITED 
 • methadone 	
 • Prohibited at study entry and throughout the study
Antimicrobials, antifungals, and antimalarials	PROHIBITED 
 • clarithromycin • erythromycin • levofloxacin • moxifloxacin • pentamidine 	
 • Prohibited at study entry and throughout the study

Medication Class	Medication ^a	Prohibition/restrictions
	
 • roxithromycin 	
	
RESTRICTED
 
 • arteminol/piperaquine • azithromycin • bedaquiline • ciprofloxacin • gemifloxacin • norfloxacin • ofloxacin • fluconazole • telavancin • telithromycin 	
 • Prohibited at Baseline but may be used during the course of the study to treat a bacterial infection (e.g., urinary tract infection, respiratory infection), post-Baseline at the discretion of the Principal Investigator. • The medications on the left are only allowed under the following conditions: 
 ○ The subject has a Baseline ECG with a QTcF <425 ms IF QRS duration is <120 ms OR ○ The subject has a QTcF <450 ms at Baseline IF QRS duration ≥120 ms

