^a Medications within each class include but are not limited to the examples listed in this table

Appendix B Prohibited and Restricted Concomitant Medications: Inhibitors and Inducers of Cytochrome P450 Enzyme 3A4

The information presented here is intended to provide guidance and does not constitute an exhaustive list of strong CYP 3A4 enzyme (CYP3A4) inhibitors and inducers. Any questions should be discussed with the Medical Monitor or appropriate designee.

The Investigator may prescribe, adjust, or discontinue appropriate medication to treat or manage AEs. Subjects who require current treatment with a prohibited medication will be withdrawn from the study.

Subjects who have previously taken a prohibited medication during the study will be withdrawn from the study unless:

- the prohibited medication has been discontinued AND
- withdrawal from the study presents an unacceptable medical risk to the subject

The justification to allow the subject to continue in the trial will be made by the Sponsor/Medical Monitor, with medical input from the Investigator, and will be documented. If a subject is allowed to remain in the trial, this will be reported as a major protocol deviation and not a waiver.

The metabolism of pimavanserin is affected by strong CYP3A4 inhibitors, resulting in an increase in maximum plasma concentration (C_{max}) and area under the plasma concentration-time curve (AUC) of approximately 3-fold.

Strong inhibitors of CYP3A4 are to be stopped at least 7 days or 5 half-lives, whichever is longer, prior to the administration of study drug. Strong inducers of CYP3A4 are to be stopped 30 days or 5 half-lives, whichever is longer, prior to the administration of study drug.

Moderate inhibitors and inducers of CYP3A4 may be allowed but should be used with caution.

STRONG INHIBITORS
	
grapefruit juice ^a boceprevir (Victrelis[®]) clarithromycin (Biaxin[®]) cobicistat (part of Stribild[®]) conivaptan (Vaprisol[®]) fluvoxamine (Luvox[®]) indinavir (Crixivan[®]) itraconazole (Sporanox[®]) ketoconazole (Nizoral[®]) lopinavir and Ritonavir (Kaletra[®]) mibefradil (Posicor[®]) nefazodone (Serzone[®])
	
MODERATE INHIBITORS
	
grapefruit juice ^a amprenavir (Agenerase[®]) aprepitant (Emend[®]) atazanavir (Reyataz[®]) ciprofloxacin (Cipro[®]) darunavir/ritonavir (Prezista[®]/ritonavir) diltiazem erythromycin (Erythrocin[®] lactobionate) fluconazole (Diflucan[®]) fosamprenavir (Lexiva[®])

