---------------------------------	--	-----------------------------------	--

STRONG INHIBITORS (continued)
	
nelfinavir (Viracept®) posaconazole (Noxafil®) quinupristin (Synercid®) ritonavir (Norvir®, part of Viekira Pak™) saquinavir (Invirase®) telaprevir (Incivek®) telithromycin (Ketek®) voriconazole (Vfend®)
		
imatinib (Gleevec®) verapamil (Calan®)

STRONG INDUCERS
	
avasimibe carbamazepine (Tegretol®) phenobarbital (Luminal®, Solfoton®) phenytoin (Dilantin®) rifampin (Rifadin®, Rifadin® IV, Rimactane®) St. John's Wort
	
MODERATE INDUCERS
	
bosentan (Tracleer®) efavirenz (Sustiva®) etravirine (Intelence®) modafinil (Provigil®) nafcillin (Unipen®, Nallpen®)

^a The effect of grapefruit juice varies widely among brands and is concentration-, dose-, and preparation-dependent. Studies have shown that it can be classified as a “strong CYP3A inhibitor” when a certain preparation was used (e.g., high dose, double strength) or as a “moderate CYP3A inhibitor” when another preparation was used (e.g., low dose, single strength). (FDA Drug Development and Drug Interactions) (<http://www.fda.gov/Drugs/DevelopmentApprovalProcess/DevelopmentResources/DrugInteractionsLabeling/ucm093664.htm#classInhibit>)

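### Protocol Appendix A allows telithromycin on study, while Appendix B lists it as a strong CYP3A4 inhibitor, a class that appears to be barred during dosing

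*Protocol*

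**What the plan says.** **Appendix A (antimicrobials, restricted row).** Telithromycin is one of ten entries under this rule: "Prohibited at Baseline but may be used during the course of the study to treat a bacterial infection". Use is at the Principal Investigator's discretion. The subject's Baseline QTcF must be below 425 ms if QRS is under 120 ms, or below 450 ms if QRS is 120 ms or more. The row does not mention CYP3A4 or refer to Appendix B.

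**Appendix B (CYP3A4 agents).** The strong-inhibitor list includes "telithromycin (Ketek" (quotation cut at the trademark sign). The text says strong inhibitors raise pimavanserin Cmax and AUC about 3-fold. They must be stopped at least 7 days or 5 half-lives, whichever is longer, before study drug. Moderate inhibitors and inducers may be allowed with caution; nothing equivalent is said of strong agents. The appendix also repeats the general rule: "Subjects who have previously taken a prohibited medication during the study will be withdrawn from the study unless" the drug has been stopped and withdrawal would carry unacceptable medical risk. For a subject who stays: "If a subject is allowed to remain in the trial, this will be reported as a major protocol deviation and not a waiver".

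**Section 4.5.2.1.** "Prohibitions and restrictions for concomitant medications should be followed between the initial Baseline visit and Visit 9/ET as specified in" both appendices. It adds: "Medications that can prolong QT interval are prohibited (or restricted if approved by the Medical Monitor) as specified in" Appendix A.

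**The concern.** The two appendices agree at entry, because neither lets a subject start study drug while on telithromycin. They part after the first dose. Appendix A gives an express, conditional permission, while Appendix B places the drug in a class that its own rules point towards excluding. No text exempts telithromycin or says which appendix prevails.

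Two things are at stake. The first is subject safety: the checks attached to the permission address QT, not a roughly 3-fold rise in pimavanserin exposure. The second is subject handling: if Appendix B bars strong inhibitors on study, a prescription that Appendix A allows is also a ground for withdrawal, or a major deviation if the subject remains.

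**Working it through.** There is no sample-size or power figure to reproduce. The check compares the two lists and then asks what Appendix B requires on study.

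**Step 1: overlap of the lists.** Appendix B has 20 strong-inhibitor entries. Four are also named in Appendix A:

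| Drug | Appendix B | Appendix A |
|---|---|---|
| clarithromycin | strong inhibitor | prohibited throughout |
| fluvoxamine | strong inhibitor | prohibited throughout |
| nefazodone (spelled nefazadone in Appendix A) | strong inhibitor | prohibited throughout |
| telithromycin | strong inhibitor | **allowed on study, with conditions** |

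Two of Appendix B's strong inducers, carbamazepine and phenytoin, are also named in Appendix A, and both are prohibited. The overlap is therefore 4 + 2 = 6 drugs: 5 prohibited and 1 not.

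**Step 2: the other restricted antimicrobials.** Of the 10 entries in that row, telithromycin is the only strong inhibitor. Ciprofloxacin and fluconazole are moderate inhibitors in Appendix B, which allows these with caution, so they do not conflict.

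**Step 3: does Appendix B reach past the first dose?** Its one explicit sentence on strong inhibitors is a washout, so an on-study bar has to be inferred. Four points support it:

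1. The title is "Appendix B Prohibited and Restricted Concomitant Medications: Inhibitors and Inducers of Cytochrome P450 Enzyme 3A4", and Section 4.5.2 says: "Concomitant medications are defined as any medication taken on or after the date of the first dose of study drug". A list of concomitant medications in that sense is not confined to the period before dosing.
2. Section 4.5.2.1 applies both appendices from Baseline to Visit 9/ET.
3. Appendix B carries the withdrawal rule for prohibited medication taken during the study, which would have little purpose in a washout-only list.
4. Only moderate agents are said to be allowable. On a washout-only reading, strong inhibitors that Appendix A does not name, such as ketoconazole or itraconazole, could be started soon after the first dose, which would defeat the washout.

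**Step 4: existing safeguards.** Medical Monitor approval in the Section 4.5.2.1 sentence on QT-prolonging drugs is a QT control. The QTcF condition uses the Baseline tracing, which may be months old when the antibiotic is given. After Week 16, scheduled ECGs are 12 weeks apart (Weeks 16, 28, 40 and 52), and Table S-1 does not mark an ECG at unscheduled visits, so a short course could fall between tracings. Section 5.1.3 bases dose adjustment on clinical response; no rule lowers the dose with a strong inhibitor.

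**Step 5: scale.** The documents give only the class-level factor of about 3. Assuming exposure is proportional to dose (not stated in the documents), exposure would resemble that of:

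- 34 mg dose: 3 × 34 = 102 mg
- 20 mg dose: 3 × 20 = 60 mg

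These figures show order of size only. No telithromycin-specific factor is given.

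**The case against.** The strongest reply is that the conflict is not written down. Appendix B calls itself guidance, and its stated rule for strong inhibitors concerns the time before study drug, which matches Appendix A's bar at Baseline. It never uses the throughout-the-study phrase that Appendix A uses repeatedly. The title assigns neither prohibited nor restricted to the strong class, and the withdrawal text is standard wording repeated from elsewhere. This stands as far as it goes: the on-study bar is an inference.

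The 3-of-4 pattern is also limited evidence. Appendix A is organised by therapeutic class and also prohibits erythromycin and modafinil, which Appendix B lists as moderate. The count shows that telithromycin is the odd one out; it does not prove why the other three are prohibited.

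A site that applied both appendices and took the stricter entry would avoid the problem, and both Section 4.5.2.1 and Appendix B invite questions to the Medical Monitor without limiting them to QT. But no precedence rule is written, and a site with an express permission in front of it has little reason to ask.

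The point survives either reading. If Appendix B bars strong inhibitors on study, the appendices conflict. If it does not, the protocol allows a drug from a class with a stated 3-fold interaction and no safeguard against that interaction.

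**Conclusion.** The concern holds and should be fixed. Telithromycin is the one drug named in both appendices that Appendix B classes as strong and Appendix A does not prohibit: 1 of 4 strong inhibitors, or 1 of 6 with strong inducers included. Following Appendix A as written leads either to an unguarded interaction or to a withdrawal or major deviation.

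The scope is narrow. The documents do not state how often the drug would be used, and it is probably seldom. The 3-fold figure is for the class. The effect is on the safety and handling of exposed subjects; no endpoint, analysis or sample size changes. The conflict between the appendices rests on reading Appendix B as governing the dosing period, but the absence of an interaction safeguard does not depend on that reading.

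**What to change.** 1. In Appendix A, move telithromycin from the restricted to the prohibited antimicrobials, beside clarithromycin. Leave ciprofloxacin and fluconazole where they are.
2. In Appendix B, after the washout sentences, add: *Strong CYP3A4 inhibitors and inducers are prohibited from the first to the last dose of study drug, not only before the first dose.*
3. Leave grapefruit juice, which is listed as both strong and moderate, under footnote a. The footnote does not tell a site which class applies to a given product, so such questions go to the Medical Monitor, as Appendix B already provides.

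The second change goes beyond telithromycin, but it only makes explicit the rule Appendix B appears to intend. The cost is one list entry and one sentence, with no added procedures. Section 10.7 requires protocol changes to go to the IRB/EC as an amendment or a notification, so this can be filed by either route or included in the next amendment.

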Table 8	Criteria for Potentially Clinically Important ECG Values.....	41

LIST OF FIGURES

Figure 1	Schematic of Study Design.....	12
----------	--------------------------------	----

ABBREVIATIONS

AE	adverse event
ATC	Anatomical Therapeutic Chemical
BMI	body mass index
CGI-S	Clinical Global Impression Scale – Severity
COVID-19	coronavirus disease 2019
C-SSRS	Columbia-Suicide Severity Rating Scale
DB	double-blind
DMP	Data Management Plan
DSMB	Data and Safety Monitoring Board
ECG	electrocardiogram
eCRF	electronic case report form
EOT	end-of-treatment
EQ-5D-5L	5-level EuroQoL-5D
ESRS-A	Extrapyramidal Symptom Rating Scale-Abbreviated
ET	early termination
GCAS	Global Clinical Assessment of Suicidality
IA	interim analysis
MedDRA	Medical Dictionary for Regulatory Activities
MMSE	Mini-Mental State Examination
Msec	Milliseconds
NPI	Neuropsychiatric Inventory
OL	open-label
PCHC	Pareto Classification of Health Change
PCI	potentially clinically important
PT	preferred term
QTcB	QT interval corrected for heart rate using Bazett’s formula
QTcF	QT interval corrected for heart rate using Fridericia’s formula
SAE	serious adverse event
SD	standard deviation
SDI	Sleep Disorders Inventory
SE	standard error
SOC	system organ class
TEAE	treatment-emergent adverse event
VAS	visual analogue scale

1 INTRODUCTION

This statistical analysis plan provides a technical and detailed elaboration of the statistical analyses of efficacy and safety data as described in the study protocol amendment 4 dated 05 March 2021. Specifications for tables, figures, and listings are contained in a separate document.

For the Czech republic, a country-specific protocol amendment (Amendment 4-CZ dated 23 July 2019) specified additional supervision requirements for subjects with mild, moderate, or severe dementia; added exclusion criteria for tachycardia and blood pressure measurements; and added temperature to list of vital signs assessments.

For Bulgaria, a country-specific protocol amendment (Amendment 3-BG dated 23 July 2019) specified that the designated study partner/caregiver must be in daily contact with the subject. This Amendment also added further details regarding the definitions of prior and concomitant therapies, and clarified the Investigator's options for the use of concomitant medications.

2 OBJECTIVES

2.1 Primary Objective

The primary objective of this study is to assess the safety and tolerability of long-term pimavanserin treatment in adult and elderly subjects with neuropsychiatric symptoms related to neurodegenerative disease.

2.1.1 Primary Endpoint

The primary safety measure for this study is treatment-emergent adverse events (TEAEs).

2.2 Secondary Objectives

Not applicable.

2.2.1 Secondary Endpoints

Not applicable.

2.3 Exploratory Objectives

The exploratory objectives of this study are:

- to explore the safety and tolerability of long-term pimavanserin treatment in adult and elderly subjects with neuropsychiatric symptoms related to neurodegenerative disease on the following:
 - suicidality

- cognition
- extrapyramidal symptoms
- to explore the benefit of long-term pimavanserin treatment in adult and elderly subjects with neuropsychiatric symptoms related to neurodegenerative disease on
 - clinical global impression of neuropsychiatric symptoms
 - quality of life
 - sleep

2.3.1 Exploratory Endpoints

The exploratory endpoints to assess the safety and tolerability of long-term treatment pimavanserin are described by:

- Columbia-Suicide Severity Rating Scale (C-SSRS) or Global Clinician Assessment of Suicidality (GCAS) scale (if the subject is not able to complete the C-SSRS in the Investigator's judgement)
- Mini-Mental State Examination (MMSE)
- Extrapyramidal Symptom Rating Scale-Abbreviated (ESRS-A)

Benefits of long-term pimavanserin treatment are described by:

- Change from Baseline in Clinical Global Impression-Severity (CGI-S) score for neuropsychiatric symptoms
- Change from Baseline in the 5-level EuroQol 5D (EQ-5D-5L) score
- Change from Baseline in Sleep Disorder Inventory (SDI) score

3 STUDY DESIGN

3.1 General Study Design

The ACP-103-047 study is a Phase 3b, open-label (OL) extension study to evaluate the long-term safety and tolerability of pimavanserin in adult and elderly subjects with neuropsychiatric symptoms related to neurodegenerative disease. This study will be conducted as a 52-week OL extension of the ACP-103-046 study (antecedent study), consisting of two periods: a 52 week OL treatment period, and a 4 week safety follow-up period. The total duration of exposure to pimavanserin may be greater than 52 weeks as subjects may have been treated with pimavanserin in the antecedent study. Approximately 100 global sites will participate in this study.

Eligible subjects will be those subjects who completed the ACP-103-046 study and, in the Investigator's judgement, may continue to benefit from longer term therapy with pimavanserin. Subject and study partner/caregiver consent for the present study must be obtained prior to the final procedures being performed at the antecedent study's end of treatment (EOT or early termination (ET) visit (if the study was ended early by the Sponsor). Data from the EOT/ET procedures of the antecedent study will be transferred over to the ACP-103-047 study for inclusion as baseline information, and this antecedent EOT visit will be considered the Baseline visit (Visit 1).

Eligible subjects will receive once daily doses of pimavanserin during the treatment period, starting with 34 mg of pimavanserin at the Baseline visit. Dose adjustments of pimavanserin down to 20 mg and up to 34 mg are permitted at any study visit (scheduled or unscheduled) after Baseline.

During the Treatment Period, clinic visits will be conducted at Baseline and Weeks 2, 4, 8, 12, 16, 28, 40 and 52 (EOT), or upon ET from the study.

[figure not shown]
Study drug will be dispensed to the subject to take home at the Baseline visit and at each subsequent visit (with the exception of Week 52). The subject and their study partner/caregiver will be provided instructions to take the first dose of study drug on the day after the Baseline visit. It is recommended that the subject take the study drug at approximately the same time each day as a single, oral dose.

All concomitant permitted medications should remain stable during the study but can be adjusted or discontinued, if clinically appropriate. These changes should be discussed with the Medical Monitor or designee as appropriate.

A safety follow-up telephone call to the subject and study partner/caregiver should at 30 (+4) days after the last dose of study drug.

Figure 1 illustrates the study design.

Figure 1 Schematic of Study Design

* Eligible subjects will begin pimavanserin dosing at 34 mg. Dose adjustments of pimavanserin down to 20 mg and up to 34 mg are permitted at any study visit (scheduled or unscheduled) after Baseline based on Investigator assessment of clinical response.

3.2 Schedule of Assessments

The schedule of events and assessments for the study is presented in [Table 1](#).

Table 1 Schedule of Events and Assessments for ACP-103-047

Visit Number	Baseline ^b	Treatment Period								Unscheduled Visit	Follow-Up ^k
	1	2	3	4	5	6	7	8	(EOT/ET) 9		10
Visit Week ^a	Week 0	Week 2	Week 4	Week 8	Week 12	Week 16	Week 28	Week 40	Week 52		Week 56
Type of visit	Clinic	Clinic	Clinic	Clinic	Clinic	Clinic	Clinic	Clinic	Clinic	Clinic	Phone call
Allowable visit window (# days)		±3	±3	±3	±3	±7	±7	±7	±7		+4
Informed consent ^b	X										
Inclusion/exclusion criteria	X										
Medical history and demographics	X										
Psychiatric, dementia, and neurological history	X										
Physical examination	X						X		X		
Vital signs	X	X	X	X	X	X	X	X	X	X	
Weight	X	X	X	X	X	X	X	X	X		
ECG ^c	X	X	X	X	X	X	X	X	X		
Clinical laboratory tests	X				X				X		
Pregnancy test ^d	X	X	X	X	X	X	X	X	X		
Urine drug screen	X				X				X		
MMSE	X	X	X	X	X	X	X	X	X		
ESRS-A	X	X	X	X	X	X	X	X	X	X	
C-SSRS ^c or GCAS ^c	X	X	X	X	X	X	X	X	X	X	
CGI-S	X	X	X	X	X	X	X	X	X	X	
EQ-5D-5L	X				X		X		X		
Sleep Disorders Inventory ^f	X				X		X		X		
Assessment of concomitant medications/procedures	X	X	X	X	X	X	X	X	X	X	X

Visit Number	Baseline ^b	Treatment Period								Follow-Up ^k	
	1	2	3	4	5	6	7	8	(EOT/ET) 9		10
Visit Week ^a	Week 0	Week 2	Week 4	Week 8	Week 12	Week 16	Week 28	Week 40	Week 52	Unscheduled Visit	Week 56
Type of visit	Clinic	Clinic	Clinic	Clinic	Clinic	Clinic	Clinic	Clinic	Clinic	Clinic	Phone call
Allowable visit window (# days)		±3	±3	±3	±3	±7	±7	±7	±7		+4
Assessment of AEs ^g	X	X	X	X	X	X	X	X	X	X	X
Dispense study drug ^h	X ^{i,j}	X	X	X	X	X	X	X		X	
Study drug accountability	X ^j	X	X	X	X	X	X	X	X	X	

Table footnotes and abbreviations on next page

Abbreviations: AE(s)=adverse event(s); CGI-S=Clinical Global Impression-Severity; C-SSRS=Columbia-Suicide Severity Rating Scale; ECG=electrocardiogram; EOT/ET=end-of-treatment/early termination; EQ-5D-5L=5-level EuroQol-5D; ESRS-A=Extrapyramidal Symptom Rating Scale - Abbreviated; GCAS=Global Clinician Assessment of Suicidality; MMSE=Mini-Mental State Examination

- ^a Study visits are designated by weeks and have a ± 3 -day window (Visits 2 through 5), or a ± 7 -day window (Visits 6 through 9), or a +4-day window (Visit 10) calculated from the Baseline Visit.
- ^b Subject and study partner/caregiver consent for the present study **must be** obtained for entry into the present study prior to the final procedures being performed at the end of treatment (EOT) visit in the antecedent study or early termination (ET) visit (if the study was ended early by the Sponsor). Data from the EOT/ET visit procedures of the antecedent study will be carried over as baseline information in the present study, as applicable.
- ^c A single 12-lead ECG can be performed any time before blood sampling or at least 30 minutes after blood sampling during clinic visits.
- ^d A urine pregnancy test may be performed for female study subjects of childbearing potential. If urine cannot be obtained in women of childbearing potential, a serum pregnancy test should be done in its place.
- ^e The scale used in the antecedent study should also be used in the ACP-103-047 study. If the subject was previously assessed with the C-SSRS and is no longer able to reliably complete the C-SSRS in the Investigator's judgment, the GCAS should be administered and used thereafter in the present study.
- ^f Appropriate consent/assent needs to be collected before assessment at Baseline.
- ^g All ongoing AEs from the antecedent study will be carried over after informed consent has been obtained for the ACP-103-047 study and recorded from Baseline for the present study until resolution or the follow-up safety assessment. AEs occurring after the first dose of open-label study drug until 30 days after the last dose of open-label study drug in the antecedent study will be recorded as an AE in the ACP-103-047 study.
- ^h Study drug will be dispensed to the subject at either scheduled or unscheduled visits.
- ⁱ Study drug will be dispensed to the subject to take home at the Baseline visit. The subject and study partner/caregiver will be provided instructions to take the first dose of study drug on the following day.
- ^j The used and unused treatment kits, blister cards, and tablets from the antecedent study are to be collected by the Investigator as part of the EOS/ET visit of the antecedent study before study drug for the present study can be dispensed.
- ^k This visit is a safety follow-up telephone call visit for subjects who complete the study or who discontinue prematurely from the study. This visit will occur 30 (+4) days after the last dose of study drug.

